Evaluation of Clinical Performance, Parent's Satisfaction, Gingival Health and Bacterial Effects of Bioflex Crowns & Endocrowns Compared to Ready-Made Zirconia Crowns on Pulpotomized Primary Molars: A Randomized Clinical Trial

A Protocol submitted to the Faculty of Dental Medicine (Boys, Cairo), Al-Azhar University, in the partial fulfillment of the requirements of Doctor Degree in Pedodontic and Oral Health

Department of Pedodontics and Oral Health,
Faculty of Dental Medicine (Boys, Cairo),
Al-Azhar University
1445 H- 2023 G

Introduction

Dental caries is the most prevalent disease, affecting 60–90% of children worldwide. If left untreated, tooth structure would be progressively damaged lead to pulpal inflammation which require pulpal therapy. Primary dentition commonly affected by caries because of improper oral hygiene and increased intake of sucrose. Nowadays, repairing and restoring primary teeth rather than extraction is receiving attention to maintain appropriate articulation and preserve the space required for the eruption of permanent teeth ⁽¹⁾.

Selecting a suitable final restoration for Pulpotomized primary molars is the key element that affects success of treatment. Stainless steel crowns (SCCs) are known to be the most protective, and durable restorations of the primary dentition with the advantages of maintaining morphologic form, superior clinical performance, effortless placement and time-efficient ⁽²⁾. Despite superior qualities of (SSCs), their use is not popular nowadays due to poor esthetic appearance, parents and child's demanding more esthetic restoration. So, several treatment options have been developed for treatment of primary teeth such as strip crowns, pre-veneered stainless-steel crowns and zirconia crown⁽³⁾.

Zirconia is being used successfully in general dentistry, due to its superior toughness and fracture resistance compared with other types of ceramics, it is a crystal-like dioxide of zirconium that possess a metal like mechanical properties and a tooth like color, that are available to use for primary teeth treatment. Pediatric zirconia crowns were introduced by EZ-pedo and became commercially available in 2008⁽⁴⁾.

Pediatric zirconia crowns are preformed and made completely with ceramic materials (tetragonal zirconia). It have high flexural strength, allowing them to resist crack propagation, high strength, toughness, higher resistance to chemicals, and superior erosion resistance, so it provided a more durable and esthetic alternative for the management of dental caries in primary molars ⁽⁵⁾.

The clinical performance, gingival status and periodontal health of pediatric zirconia crowns versus stainless steel crowns were evaluated in several studies ⁽⁶⁻⁹⁾, and showed that zirconia crown had more clinical performance, gingival and periodontal health than that of stainless steel crowns, However, the amount of tooth reduction needed to receive zirconia

crown (determinant factor for passive fitting) is more aggressive than that required for stainless steel crowns by approximately 20 to 30%. So there is a need for developing more flexible esthetic restorations⁽⁶⁾.

Bioflex crowns are available as aesthetic preformed pediatric crowns that are flexible, durable, and adaptable offering properties of both stainless steel and zirconia crowns. There is a lack of literary evidence for assessment of the properties of Bioflex crowns and their effect on clinical outcomes and parental satisfaction compared to traditionally available options⁽¹⁰⁾.

More conservative treatment modalities preserving natural tooth structure (minimal intervention dentistry) have been considered aided by simultaneous progress in biological research and development of adhesive materials. Endocrowns were first described in 1999 by Bindl and Mörmann considered one of these strategies⁽¹¹⁾. Endocrowns are monolithic adhesive ceramic restorations give the opportunity of color matching, and shade selection that is not available in ZC⁽¹²⁾.

Endocrowns need a special preparation design with less circumferential tooth reduction including a butt joint preparation at the cervical margin that ends supragingival so eliminates any possible discomfort or gingival trauma during tooth reduction offering healthier periodontal tissues, more peripheral enamel preservation, and an increase in the surface area for bonding. In contrast, the finishing line of ZC must extend for 1 to 2 mm subgingivally. But the occlusal surface reduction is similar for both restorations⁽⁴⁾. Endocrown retention is gained macro-mechanically by friction with the pulpal walls, and micromechanically through adhesive cementation⁽¹²⁾.

Endocrowns are considered as effective restorations for molars that have undergone endodontic treatment offering better fracture resistance and stress distribution, offer excellent strength for cuspal overlays, it can be used as a final restoration for primary molars preserve tooth structure, and maintain periodontal health⁽¹³⁾.

Up to our knowledge, there is no study evaluate the clinical performance, bacterial adherence, assessment of dental plaque and gingival status of endocrowns and Bioflex crowns as a new restorative modality in Pulpotomized primary molars compared with prefabricated ZCs, and the parental satisfaction toward the three restorations at the end of the 12 month follow-up

Aim of the study

This study will be conducted to evaluate clinical performance, parent's satisfaction, gingival health and bacterial effects of Bioflex crowns & Endocrowns compared to ready-made zirconia Crowns on Pulpotomized primary molars

Patients and Methods

Study Design:

This study will be designed as a randomized clinical trial

Sample Size calculation: ^(7,13)

This study will be conducted to evaluate Clinical performance, bacterial adherence, assessment of gingival health and patient satisfaction of LS2 endocrowns and Bioflex crowns compared with prefabricated zirconia

crowns as a restoration of Pulpotomized primary molars. Assuming there is no difference between groups (equivalence trial), if there is truly no difference between the standard and experimental treatments, then 22 patients in each group are required to be 80% sure that the limits of a two-sided 95% confidence interval will exclude a difference in means of more than 0.6. This number is to be increased to 24 in each group to compensate for possible losses during follow up. Sample size was calculated by sealed envelope power calculator.

Study Setting and Population:

This study will involve children with 72 primary molars who require Pulpotomy treatment at the Pedodontics and Oral Health Department, Faculty of Dental Medicine (Boys, Cairo), Al-Azhar University.

Subject grouping:

The involved primary molars (n= 72) will be divided randomly into 3 groups (n=24) according to the type of the final restoration for Pulpotomized molars as the following

- **Group A:** will be restored with endocrown (study group)
- **Group B:** will be restored with prefabricated Bioflex crown (study group).
- **Group C:** will be restored with prefabricated zirconia crown (control group).

Eligibility criteria for the study:

Inclusion criteria: ⁽¹²⁾

- Parents' and patients' acceptance and cooperation (frankel scale +ve.++ve)

- Apparently Healthy children.
- Child's age ranging from 4 to 8 years old.
- Primary 2nd molars with deep carious lesion indicated for vital Pulpotomy
- No periapical pathological lesion
- No root resorption exceeding more than 2/3 of root length.

Exclusion criteria ⁽¹²⁾

- Medically compromised children (bleeding disorders, cardiac patient and any systemic diseases could affect oral and gingival health.
- Presence of para-functional habits. Such bruxism.
- Non-restorable tooth.
- Teeth with non-vital pulp

Ethical Consideration:

- This study will be carried out after approval of the Ethical Committee, Faculty of Dental Medicine (Boys, Cairo), AL-Azhar University.
- All children's parents/ guardians will be informed in a verbal and written manner about the aim of these research. A written informed consent will be signed by the parents before starting the study

Intervention:

Pulpectomy Procedures ⁽¹²⁾

- The tooth will be anaesthetized. Then, it will be isolated using a rubber dam.
- Caries will be removed with a sterile non-end cutting bur # 558 to complete the removal of the pulp chamber roof under copious water coolant spray. Coronal pulp tissue remnants will be removed with a sharp, sterile excavator. A piece of cotton soaked with formocresol will be inserted into the pulp chamber for 5 minutes.

- After removing the formocresol pellet, a thick mix of zinc-oxide/eugenol paste will be packed into the pulp chamber to seal the orifices.

Restoration of the tooth:

According to the groups restoration will be as the following:

Group A: Endocrowns tooth preparation, scanning, cementation:

For the endocrowns ^(12, 13)

- A layer of light -cured glass ionomer cement ° of 1 mm thickness will be applied over the ZOE- to isolate it from the successive resin based restorations and adhesives- leaving a minimum of 3 mm of the pulp chamber to provide an adequate thickness for the endocrown core.
- Round-end tapered stone will be used to achieve depth cuts of 1.5 mm for occlusal clearance
- A wheel stone will complete the occlusal reduction and making butt joint finish line.
- Tapered stone of 8-degree angle will be used to prepare axial wall flared, the pulp chamber walls to a standard degree of divergence.
- Abrasive rubber tip will be used to smoothening and rounding the internal angles giving a polished and smoothed preparation.
- Endocrown will be manufactured using CAD/CAM technology
- internal wall of crown will be treated with etchant material, rinsed, dried then silane coupling agent

- Dual-cure resin cement will be applied on the crown fitting surface for endocrown cementation.

Group B: Preformed Bioflex crowns ⁽¹⁰⁾

According to manufacturer instruction the preparation will be as the follow:

- Light -cured glass ionomer filling of adequate thickness will be applied over the ZOE to seal the cavity before preparation
- A digital caliper will be used to measure a mesio-distal dimension of tooth then suitable sized preformed crown will be selected.
- Tooth preparation will be carried out with a tapered diamond bur for occlusal reduction by 1–1.5 mm, including the central groove.
- The proximal preparation will be around 0.5 mm to clear the contact area
- Placement of the crown will be achieved by a snug fit followed by contouring using a Hover's plier.
- Crown cementation will be carried out using glass ionomer cement and removal of excess cement using floss or explorer.

Group C: performed zirconia crowns ^(10, 12, 13)

- Light -cured glass ionomer filling of adequate thickness will be applied over the ZOE to seal the cavity before preparation.
- A digital caliper will be used to measure a mesio-distal dimension of tooth then suitable sized preformed crown will be selected.

- A diamond bur will reduce the occlusal surface by 1.5–2 mm
- Interproximal contacts will be prepared with a tapered fissure bur. About 1–2 mm sub gingival preparation will be performed
- The selected crown will be placed and checked.
- The passive fit of the crown will be assessed and will be luted with glass ionomer cement.
- Consistent firm finger pressure will be applied during cementation.

Observations:

Clinical Performance Assessment ^(10,12)

- Retention, marginal adaption, fracture of the restoration were scored using a modified United States Public Health Service (USPHS) criterion.
- Dental plaque accumulation and gingival condition were assessed using plaque index (PI) and GI.
- Preparation time and cementation assessment using stop watch to record time from preparation start till final restoration cementation.⁽¹⁵⁾
- Clinical performance and oral status will be assessed at follow-up periods of 3 (T1), 6 (T2), and 12 (T3) months. At the end of the follow-up (T3), parent's satisfaction analysis toward the color, shape, and size of three restorations will be adopted to directly evaluate their satisfaction toward their children's restorations. Parents' responses were rated on a 5-point Likert-type scale.

Microbiological analysis: ⁽⁹⁾

- The swabs will be collected before preparation of crowns, 3 months, 6 months and 12 months after cementation.
- The number of Streptococcus Mutans, lactobacillus will be digitally counted.
- Swabs will be taken from occlusal surface by means of the tips of sterile cotton
- All specimens were transported immediately to microbiological lab.
- Swabs will be taken from occlusal surface by means of the tips of sterile cotton.
- Samples will be preserved in a transporting medium tube containing 9ml thioglycolate broth medium.
- The number of Streptococcus Mutans, lactobacillus will be digitally counted.

Data Management and Analysis

Data will be analyzed using IBM SPSS advanced statistics (Statistical Package for Social Sciences), version 27 (SPSS Inc., Chicago, IL). Numerical data will be described as mean and standard deviation or median and range. Data will be explored for normality using Kolmogorov-Smirnov test and Shapiro-Wilk test. Comparisons between 3 groups for normally distributed numeric variables will be done using the ANOVA while for non-normally distributed numeric variables will be done by Kruskal Wallis test. An equivalence limit will be checked in the difference between groups. Categorical data will be described as numbers and percentages and comparisons will be done by chi square test or fisher exact as appropriate. A p-value less than or equal to 0.05 will be considered statistically significant. All tests will be two tailed.

References

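### The equivalence margin of 0.6 is tied to no outcome, visit, scale or SD, and the analysis section does not carry the implied confidence-interval rule into a test

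*Combined protocol and SAP*

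**What the plan says.** **Sizing.** The Sample Size calculation section lists four domains (clinical performance, bacterial adherence, gingival health, satisfaction). It calls the trial an equivalence trial, assumes no true difference between a standard and an experimental treatment, and gives 22 patients per group to be "80% sure that the limits of a two-sided 95% confidence interval will exclude a difference in means of more than 0.6". On method it says "Sample size was calculated by sealed envelope power calculator". The section heading also cites references 7 and 13. No SD is printed. On losses: "This number is to be increased to 24 in each group to compensate for possible losses during follow up".

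**Groups.** Subject grouping defines two study groups (endocrown, Bioflex) and one control (zirconia).

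**Measures.** The Observations section lists about nine:
- three scored items: "Retention, marginal adaption, fracture of the restoration were scored using a modified United States Public Health Service (USPHS) criterion";
- two indices: "Dental plaque accumulation and gingival condition were assessed using plaque index (PI) and GI";
- stopwatch time for preparation and cementation;
- parental satisfaction at 12 months, where "responses were rated on a 5-point Likert-type scale";
- two bacterial counts: "The number of Streptococcus Mutans, lactobacillus will be digitally counted".

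On timing, "Clinical performance and oral status will be assessed at follow-up periods of 3 (T1), 6 (T2), and 12 (T3) months". Swabs are taken before preparation and at the same three follow-up visits.

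**Analysis.** Data Management and Analysis compares the three groups by ANOVA or, for non-normal data, Kruskal-Wallis, and categorical data by chi-square or Fisher, two-tailed at 0.05. One further sentence says that an equivalence limit will be checked in the between-group difference. It gives no value, confidence level, outcome, visit or pair.

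**The concern.** An equivalence margin has meaning only on a stated scale. A difference of 0.6 on a plaque or gingival index, on a 5-point satisfaction scale, in stopwatch time and in a bacterial count are four different things. With no primary outcome named, 0.6 could be applied to whichever measure and visit turn out to suit it.

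The analysis section does not close the gap. The tests it names ask whether the groups differ, and failing to find a difference does not show equivalence. Kruskal-Wallis does not even produce a mean difference to set against 0.6. Since the choice between ANOVA and Kruskal-Wallis depends on a normality test, the data could decide whether the margin can be applied at all.

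At stake is whether an equivalence claim for either new crown can be traced to a rule fixed in advance, and whether the stated 80% describes the chance of meeting any objective.

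**Working it through.** **1. Inputs.** From the Sample Size calculation section: n = 22 per group, power 80%, two-sided 95% CI, margin 0.6, true difference 0. The SD is not given, so 22 cannot be reproduced from the printed inputs. It can only be solved backwards.

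**2. Back-solving the SD.** Usual normal formula for equivalence of two means (the plan prints none):

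n = 2·SD²·(z₀.₉₇₅ + z₀.₉₀)² / 0.6², with (1.960 + 1.282)² = 10.507.

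- SD 0.60: n = 21.01, rounded up to 22.
- SD 0.61: n = 21.72, rounded up to 22.
- SD 0.62: n = 22.44, rounded up to 23.

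Rounding up to 22 requires an SD of 0.600 to 0.614, so the margin is about one SD. Variants fit the wording less well: a 90% CI would imply an SD of up to 0.68, and not halving beta up to 0.71.

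**3. Power for one pair at 22.** Same formula: power = 2Φ(0.6/(SD·√(2/22)) − 1.960) − 1.

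- SD 0.60: standard error 0.181; 3.317 − 1.960 = 1.357; power 82.5%.
- SD 0.614: standard error 0.185; 3.242 − 1.960 = 1.282; power 80.0%.

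A t-based calculation, which allows for estimating the SD, gives 79.9% and 77.2%. The two methods should not be mixed without saying so.

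**4. Power if both new crowns must be equivalent to zirconia.** The two comparisons share the zirconia arm. The t-based figures pool the variance over three groups.

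| n per group | SD | Normal | t-based |
|---|---|---|---|
| 22 | 0.60 | 70.5% | 68.1% |
| 22 | 0.614 | 66.6% | 64.2% |
| 24 (no losses) | 0.60 | 77.1% | 75.2% |
| 24 (no losses) | 0.614 | 73.7% | 71.7% |

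**5. Dependence on the missing SD (assumed values).** One-pair power at 22, normal formula: 62.3% at SD 0.7 and 40.2% at SD 0.8. The same formula would then ask for 29 and 38 per group.

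**6. Why a test of difference cannot stand in (illustration).** Suppose one new crown truly differs from the other two groups by 0.6, the margin itself. At 22 per group, ANOVA would still be non-significant 7%, 17% or 29% of the time at SD 0.6, 0.7 or 0.8. The 95% CI rule would wrongly declare that crown equivalent at most 2.5% of the time.

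**7. Scored clinical items.** Assume retention, marginal adaptation and fracture are each reduced to pass/fail, which the plan does not state. With 0 failures in 22, the Wilson upper limit is 1.960²/(22 + 1.960²) = 3.84/25.84 = 14.9%. The Newcombe 95% CI for 0 versus 0 is therefore ±14.9 percentage points.

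**The case against.** Several counter-arguments are sound and limit the point.

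- **A criterion exists.** The sizing sentence describes confidence-interval inclusion, a recognised equivalence procedure, and the analysis section does mention an equivalence limit. A reader might infer that the plan has no equivalence criterion at all. That goes too far. What is missing is the link from the criterion to an outcome, a visit and the analysis.
- **The pairs can be inferred.** The study and control labels, and an aim that compares both new crowns with zirconia, point to endocrown versus zirconia and Bioflex versus zirconia. Only whether both must succeed is left open.
- **Sources are cited.** The heading cites references 7 and 13, and a methods paper on sample sizes for Normal data is in the reference list. The SD may come from one of these. It is not restated in the protocol, which is all that can be said. The titles do not settle the outcome: one study concerns clinical performance and parental satisfaction with crowns on anterior teeth, the other fracture resistance in vitro.
- **No misuse is announced.** A reader might infer that a non-significant ANOVA will be taken as equivalence. The plan does not say so, and step 6 only illustrates why it should rule this out.
- **Power depends on method.** By the formula used to infer the SD, one-pair power at 22 is at least 80%. The figures below 80% come from the t-based method.

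None of this supplies the outcome, visit, scale or SD to which 0.6 belongs, or carries the rule into the analysis section.

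**Conclusion.** The point holds in this form: the protocol sizes for equivalence but does not identify the outcome, visit, scale or SD behind 0.6, and its analysis section names tests that cannot establish equivalence, beside an equivalence check with no content. Followed as written, the outcome and visit on which equivalence is claimed stay open until results are seen.

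The documents do not show that 22 per group is wrong or that the trial is underpowered. The number is attainable at an SD of 0.600 to 0.614. On that inferred SD the 80% covers one pair. Requiring both crowns to succeed lowers it to 66.6% to 70.5% (normal) or 64.2% to 68.1% (t-based) at 22 per group.

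These figures assume zero true differences, a common SD and independent observations. The last needs care, because the sizing counts patients while the randomisation is of molars. The plan should be changed, but this does not call the design itself into question.

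**What to change.** Before any outcome data are examined:

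1. Name the single primary outcome and visit to which 0.6 applies, with its scale, SD and the source of that SD. If the records of the calculation do not identify one, choose it then.
2. In Data Management and Analysis, judge equivalence on that outcome by whether the two-sided 95% CI for the mean difference lies within ±0.6, for endocrown minus zirconia and for Bioflex minus zirconia, whatever the normality test shows.
3. State that the 80% is per comparison, say whether both crowns must succeed, and restate power from the disclosed SD, naming the method (normal or t-based).
4. Label all other outcomes secondary, and state that a non-significant ANOVA, Kruskal-Wallis, chi-square or Fisher test will not be read as equivalence.
5. If the USPHS items are analysed as pass/fail, report risk differences with 95% CIs for each new crown versus zirconia. Say that even with no failures at 22 per group the interval is about ±15 points, so equivalence on them is not established.

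The cost is protocol wording, a less favourable power statement and fewer confirmatory claims. No patients or visits are added, provided the restated power is accepted.

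### Plaque and gingival indices have no pre-treatment score; the randomised comparison stays valid, but precision, a check on imbalance and a description of change are given up

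*Combined protocol and SAP*

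**What the plan says.** The Aim of the study lists gingival health among its outcomes and frames it as a comparison with zirconia: "evaluate clinical performance, parent's satisfaction, gingival health and bacterial effects of Bioflex crowns & Endocrowns compared to ready-made zirconia Crowns".

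Under Observations, Clinical Performance Assessment, the instruments are named: "Dental plaque accumulation and gingival condition were assessed using plaque index (PI) and GI". The schedule follows in the same section: "Clinical performance and oral status will be assessed at follow-up periods of 3 (T1), 6 (T2), and 12 (T3) months". Visit labels begin at T1, no T0 is defined, and no other section places a PI or GI score before the crown.

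The Microbiological analysis section treats its outcome differently: "The swabs will be collected before preparation of crowns, 3 months, 6 months and 12 months after cementation".

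The only gingiva-related eligibility rule is the exclusion of "any systemic diseases could affect oral and gingival health". No local plaque or gingival threshold is set, and no hygiene run-in is described.

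Subject grouping makes the allocation random: "The involved primary molars (n= 72) will be divided randomly into 3 groups (n=24" per group). Data Management and Analysis plans group comparisons without a baseline term: "Comparisons between 3 groups for normally distributed numeric variables will be done using the ANOVA", with Kruskal-Wallis for non-normal variables.

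**The concern.** Children enter with a deeply carious second primary molar, and the Introduction itself links caries in the primary dentition to poor oral hygiene. Plaque and gingival inflammation around the index tooth can therefore be expected to differ between children before any crown is placed. Nothing in eligibility narrows that spread.

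Without a pre-treatment score, three things are unavailable:

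- a baseline table showing whether the three arms started alike on PI and GI;
- an adjusted comparison, which would remove the part of follow-up variation that starting status explains;
- any statement of how PI or GI moved from before treatment to follow-up.

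The swab schedule shows that a pre-treatment measurement was thought of for the bacterial outcome, so the gap looks like an omission for the gingival one. It cannot be repaired at analysis: a score not taken before treatment is gone.

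**Working it through.** **The plan's own figure.** Sample Size calculation gives 22 per group (24 after allowing for losses), from a margin of 0.6, 80% power and a two-sided 95% interval. No SD is stated and the outcome behind the margin is not named, so 22 cannot be reproduced. Working backwards with n = 2 × [SD × (1.960 + 1.282) / 0.6]², 22 per group results only if the SD is about 0.600 to 0.614. The present point does not depend on that figure. Results below are in SD units of the index concerned and are not set against the 0.6 margin, because the documents do not tie the margin to PI or GI.

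**Inputs.** From the documents: 22 molars per group analysed (24 allocated), three groups, random allocation. Assumed: a baseline-to-follow-up correlation r of 0.3 to 0.6, equal SDs at baseline and follow-up, and molars treated as independent.

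**Step 1. Chance difference in starting status between two arms.**
- SE = √(1/22 + 1/22) = 0.3015 SD.
- 95% range = ±1.96 × 0.3015 = ±0.59 SD.
- Probability that a given pair starts more than 0.3 SD apart = P(|Z| > 0.3/0.3015) = 0.32.
- With 24 per group: SE = √(2/24) = 0.289 SD, 95% range ±0.57 SD.

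**Step 2. How much reaches the follow-up comparison.** Only r times the baseline imbalance carries over. For an imbalance of 0.3 SD:
- r = 0.3: 0.3 × 0.3 = 0.09 SD.
- r = 0.6: 0.6 × 0.3 = 0.18 SD.

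Both are smaller than the 0.30 SD standard error of the unadjusted follow-up comparison, which already includes this source of variation.

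**Step 3. What adjustment would gain.** Residual variance falls by r², and interval width is multiplied by √(1 − r²).

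| r | Variance removed | Width factor | 95% half-width, 22 per group |
|---|---|---|---|
| none | 0% | 1 | 0.59 SD |
| 0.3 | 9% | √0.91 = 0.954 | 0.591 × 0.954 = 0.56 SD |
| 0.6 | 36% | √0.64 = 0.80 | 0.591 × 0.80 = 0.47 SD |

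The interval narrows by about 5% to 20%. No larger sample is needed to obtain this.

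**The case against.** A reader might infer that a GI difference at 3, 6 or 12 months mixes the crown's effect with gingivitis the child already had, so that the gingival objective cannot be answered. The documents do not support that. Molars are allocated at random, so the between-crown contrast is unbiased in expectation, and chance differences in starting status are already part of its standard error.

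A reader might also take the question to be whether each crown improved or worsened the gingiva. The stated aim is a comparison with zirconia crowns, which post-treatment scores can answer; change within a crown type is not a stated objective. Nor can baseline imbalance be called large relative to crown effects, since the documents give no PI or GI effect size or SD.

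Other objections also have force:

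- The raw imbalance of 0.3 to 0.59 SD overstates the distortion at follow-up, because only r times it carries over. The correlation may be below the assumed range: the carious surface is removed and replaced by a crown, and the zirconia arm has subgingival preparation.
- Change from baseline would not isolate a crown effect. It also contains caries removal, pulpotomy and regression to the mean, and there is no uncrowned comparison group.
- The swab is taken from the occlusal surface, so the plan does not show that the gingival margin is examined at that contact. That no extra visit would be needed is a reasonable inference, not a documented fact.

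These points limit the consequence and shape the fix. They do not remove the omission: no PI or GI baseline is scheduled, and the modest gains from one are forgone.

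**Conclusion.** The point holds as a cheap improvement of minor severity. The omission is clear from the schedule and from its contrast with the swabs. The randomised comparison of PI and GI at T1 to T3 remains valid without a baseline. The loss is confined to precision (about 5% to 20% of interval width), the ability to see or adjust for chance imbalance (standard error 0.30 SD between two arms of 22), and any description of change from before treatment.

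The imbalance figures follow from the planned group size, taking molars as independent. The precision and carry-over figures also rest on the assumed correlation of 0.3 to 0.6; a lower value would make the gain smaller.

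**What to change.** In the schedule sentence under Observations, state that PI and GI will be scored on the index molar at T0 and again at 3, 6 and 12 months. Define T0 as before anaesthesia, rubber-dam isolation and any preparation, at the visit of the first swab where possible. Saying only that the score precedes crown preparation would not be enough: under Intervention, anaesthesia and isolation for the pulp treatment come first, so a score could meet that wording after the gingiva had been handled.

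In Data Management and Analysis, add that groups will be compared on PI and GI at T1 to T3 adjusted for the T0 value, by ANCOVA or a rank-based version if the data are not normal. Show T0 values by group in the baseline table. Report change from T0 by group as descriptive only, for the reasons given above.

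The cost is a few minutes of chair time before treatment and one covariate. No additional patients are needed. The change has to be in place before a molar is treated, since its baseline cannot be recovered afterwards.

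### The bacterial count taken before crown preparation has no stated role in the analysis, so precision may be lost; its timing must be fixed before it can serve as a covariate

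*Combined protocol and SAP*

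**What the plan says.** The Microbiological analysis section sets four sampling times: "The swabs will be collected before preparation of crowns, 3 months, 6 months and 12 months after cementation". S. mutans and lactobacillus are counted at each. On the method it says: "Swabs will be taken from occlusal surface by means of the tips of sterile cotton".

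The only analysis text is the Data Management and Analysis section. It says "Comparisons between 3 groups for normally distributed numeric variables will be done using the ANOVA", and that the comparison "for non-normally distributed numeric variables will be done by Kruskal Wallis test". It adds: "An equivalence limit will be checked in the difference between groups". It names no covariate, change score, repeated-measures term or analysis visit for the counts.

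The Sample Size calculation section arrives at 22 per group and continues: "This number is to be increased to 24 in each group to compensate for possible losses during follow up". With three groups of 24, there are 72 molars.

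**The concern.** Bacterial effects are in the title and the aim of the trial. In a randomized comparison, a pre-treatment value of the same outcome can remove part of the residual variance at almost no cost. Here that value is already to be collected, but the analysis as written does not say what is done with it. If it is ignored, the intervals for the differences from zirconia may be wider than they need to be. If the counts are not normal and Kruskal-Wallis is used, that test takes no covariate and does not by itself give a between-group difference or interval.

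There is also a matter of order. A covariate is safe only if allocation cannot affect it. The plan places the first swab before crown preparation, but does not place it relative to the steps that come before preparation, and one of those differs by group.

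**Working it through.** **1. Where the first swab falls.** These are the steps listed before crown preparation:

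- All groups (Pulpectomy Procedures): caries removal, removal of coronal pulp, formocresol, then zinc-oxide/eugenol.
- Group A (Restoration of the tooth): a 1 mm glass ionomer layer, leaving at least 3 mm of the pulp chamber. It is listed ahead of the depth cuts.
- Groups B and C (same section): a glass ionomer filling that seals the cavity, expressly before preparation.

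A swab at the start of the visit precedes all of these. A swab just before the bur is used would follow a step that differs by group, and the count could then be affected by allocation. The text fits both readings.

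**2. The plan's own figure.** The plan gives no precision figure for bacterial counts. Its 22 per group is for a limit of 0.6 on an unnamed outcome, with no SD stated. With an assumed SD of 0.6, n = 2 × 0.6² × (z₀.₉₇₅ + z₀.₉₀)² / 0.6² = 2 × 10.507 = 21.01, which rounds up to 22. Nothing below depends on this.

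**3. Inputs for the precision check.** From the documents: three arms, n = 24 per arm (22 after the planned losses), two-sided 95% intervals. Assumed: independent molars, a common SD taken as the unit (on the log10 scale), a linear relation between first and later counts, and r over a range.

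**4. Formulas, for one contrast with zirconia.**

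- Unadjusted half-width: t(0.975, 3n − 3) × √(2/n).
- Adjusted half-width: t(0.975, 3n − 4) × √[(2/n)(1 − r²)(1 + 1/(3n − 5))]. The last factor is the expected cost of chance imbalance in the covariate.

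At n = 24 the unadjusted value is 1.9949 × 0.2887 = 0.576 SD. The adjusted value at r = 0 is 1.9955 × 0.2887 × √(1 + 1/67) = 0.580 SD. For other r, multiply by √(1 − r²).

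| r | n = 24, adjusted (unadjusted 0.576) | Ratio at n = 24 | Equivalent unadjusted n per arm, 24/ratio² | n = 22, adjusted (unadjusted 0.602) |
|---|---|---|---|---|
| 0 | 0.580 | 1.008 | 23.6 | 0.608 |
| 0.1 | 0.577 | 1.003 | 23.9 | 0.605 |
| 0.2 | 0.569 | 0.987 | 24.6 | 0.595 |
| 0.3 | 0.554 | 0.961 | 26.0 | 0.580 |
| 0.5 | 0.503 | 0.873 | 31.5 | 0.526 |
| 0.7 | 0.414 | 0.720 | 46.3 | 0.434 |

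Break-even is where the two half-widths are equal: r = √[1 − (0.5759/0.5803)²], about 0.12 at n = 24. The same calculation gives about 0.13 at n = 22.

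**5. Validity of the unadjusted tests.** In simulations of 100,000 trials per setting with no true difference, normal log10 counts and independent molars, the rejection rate at the 5% level was 4.9–5.1% for ANOVA, 4.7–4.9% for Kruskal-Wallis and 4.9–5.1% for ANCOVA.

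**6. Change from baseline is not an equal substitute.** Its variance is 2(1 − r) times that of the follow-up value alone: 1.4 at r = 0.3, 1.0 at r = 0.5 and 0.6 at r = 0.7. Below r = 0.5 it is less precise than ignoring the first count.

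**The case against.** The strongest reply is that the gain may be nothing. The plan gives no r, the swabbed surface changes from tooth to crown, and up to r = 0.3 the interval narrows by at most 4%, worth about two molars per arm. Nothing in the documents supports r of 0.5 or 0.7. This stands, and it limits the point to an efficiency improvement of unknown size. It does not remove the point, because the worst loss shown is 0.8% of the interval width.

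A second reply is that ANOVA on numeric variables could be meant to cover change scores. The text does not exclude that, so the fair statement is that the role of the first count is not stated.

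A third is that the timing question may require more than wording. That also stands: it must be settled before the covariate is used.

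A reader might go further in three ways that the documents do not support:

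- The inclusion criterion "Primary 2nd molars with deep carious lesion indicated for vital Pulpotomy" invites the inference that the first swab comes from a carious surface. Caries removal and filling are listed before crown preparation, so the state of the tooth at that swab is not established.
- The planned equivalence check invites the inference that wider intervals put the 0.6 limit for bacterial counts at risk. Neither the limit nor the check names an outcome, so no such link can be drawn.
- "Clinical performance and oral status will be assessed at follow-up periods of 3 (T1), 6 (T2), and 12 (T3) months" lists no pre-treatment visit, which might suggest that baseline plaque and gingival scores should be added. That would be new data collection with an unquantified gain, and is not part of this point.

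**Conclusion.** The concern holds as a matter of efficiency and pre-specification. The first bacterial count is collected and has no stated role. A reader might infer that the planned comparison is biased or has the wrong error rate; it does not, given randomization and independent molars. (The plan speaks both of children with 72 molars and of patients per group, so independence is an assumption here.)

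The possible gain at 24 per arm runs from a slight loss at r = 0 to an interval 28% narrower at r = 0.7, with no gain below r of about 0.12. The documents do not show where in that range the trial lies, and a low r is plausible. Adjustment is sound only if the first swab precedes every group-specific step.

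**What to change.** In this order:

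1. As a precondition, state in the Microbiological analysis section that the first swab is taken at the same point in all groups, before any group-specific step, including the glass ionomer step.
2. In the Data Management and Analysis section, specify log10 counts with a stated rule for zeros. Analyse them by ANCOVA at a named visit, or by a mixed model over 3, 6 and 12 months, with the first log10 count as covariate. Report endocrown minus zirconia and Bioflex minus zirconia with 95% confidence intervals.

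If the first swab is already planned ahead of the group-specific steps, the cost is wording only. If it is not, the swab has to be moved, which is a procedural change. The statistical cost is one degree of freedom: the interval is 0.8% wider at r = 0 and 0.3% wider at r = 0.1. No further children or measurements are needed.
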